#### **3.3.1.2 Exclusion Criteria**

1. Subjects participating in any drug or device clinical investigation within two weeks prior to entry into this study and/or during the period of study participation
2. Subjects who are women of childbearing potential (those who are not surgically sterilized or postmenopausal) are excluded from participation in the investigation if they meet any one of the following conditions:
  - she is currently pregnant
  - she plans to become pregnant during the study
  - she is breastfeeding

3. Subjects with any systemic disease currently affecting ocular health or which in the Investigator's opinion may have an effect on ocular health during the course of the study.
4. Subjects using any systemic or topical medications that will, in the Investigator's opinion, affect ocular physiology or lens performance.
5. Subjects with an active ocular disease or who are using any ocular medication.
6. Subjects who are not correctable to 32 letters (0.3 logMAR) in each eye with soft spherical contact lenses.
7. Subjects who currently wear monovision or multifocal contact lenses.
8. Subjects with refractive astigmatism of 0.75 D or greater in either eye.
9. Subjects who are current Acuvue Oasys wearers who have previously been unsuccessful in wearing Acuvue Vita and/or Ultra contact lenses.
10. Subjects with anisometropia (spherical equivalent) of greater than 2.00 D.
11. Subjects with any grade 2 or greater finding during the slit lamp examination (refer to Appendix B for methods of clinical evaluation). Subjects with corneal infiltrates, of ANY GRADE, are not eligible.
12. Subjects with any "Present" finding during the slit lamp examination (refer to Appendix B for methods of clinical evaluation) that, in the Investigator's judgment, interferes with contact lens wear.
13. Subjects with any scar or neovascularization within the central 6 mm of the cornea. Subjects with minor peripheral corneal scarring (that does not extend into the central area), that in the Investigator's judgment, does not interfere with contact lens wear, are eligible for this study.
14. Subjects who are aphakic.
15. Subjects who are amblyopic.
16. Subjects who have had any corneal surgery (e.g., refractive surgery).
17. Subjects who meet any of the following criteria:
  - the subject is an employee of the investigative site
  - the subject, or a member of the subject's household, is an employee of a marketing research firm

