### **3.3.3 Subject Discontinuation**

A subject MAY be discontinued (at the discretion of the Investigator, the Sponsor, and/or the IRB/EC) prior to the final study visit for a variety of reasons, including, but not limited to:

- an AE occurring during the course of the study, which precludes continued treatment or follow-up
- persistent grade 3 or 4 slit lamp findings (must be reported to the Sponsor within 24 hours)
- persistent study related symptoms/complaints
- unacceptable distance lens visual acuity (VA)
- unacceptable lens centration
- unacceptable lens movement

A subject MUST be discontinued prior to the final study visit for any of the following reasons:

- voluntary withdrawal
- death
- Investigator decision that it is not in the best medical interest of the subject to continue participation in the investigation
- ineligible at baseline- does not meet the eligibility criteria in the protocol
- inability to maintain recommended wearing schedule
- lack of motivation
- continued failure to follow subject instructions
- subject missed the 2-Week Follow-up Visit
- lost to follow-up (refer to Section 3.3.5)
- instillation of non-medically indicated solution not specified in the protocol
- other eye is discontinued
- becomes pregnant during the study

Prior to discontinuing a subject, every effort should be made to contact the subject, schedule a final study visit, obtain as much follow-up data as possible, and to retrieve all study materials. Adverse events will be followed as described in Section 6. Subject discontinuations will be documented clearly on the source document and applicable electronic CRF (e-CRF). The Investigator should indicate the PRIMARY (one) reason that the subject was discontinued for each eye. Subjects that are discontinued from the study following randomization will not be replaced.

Exit Visit assessments should be completed for early terminated subjects.

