### 5.2.3 2-Week Follow-up Visit

*NOTE: All VA measurements MUST be made using a phoropter.*

*NOTE: If Take-Home Lens Performance Surveys are not completed upon arrival, the second week survey MUST be completed at the visit. The Investigator or designee must review the Surveys for completeness before the subject leaves the office.*

*NOTE: If the subject misses this visit, they MUST be discontinued.*

- a. Collect the following lens information from the subject:
- average daily wearing time
  - average hours of comfortable wear
  - total number of days of lens wear
- b. Complete the Symptoms/Complaints section for the subject's responses **using the Rating Scale included in initial shipment.**
- c. If the subject did not come to the visit wearing one or more study lenses, go to step e. Otherwise, evaluate the lenses (while on eye), and record the following assessments:
- The Investigator or designees will ask and record the subject's responses to the Lens Performance Survey (100-point scales).
  - distance lens VA

Study ROC2-17-014 - Protocol

- over-refraction and distance VA
- lens wettability
- lens deposits
- lens centration
- lens movement

For each eye, compare the high contrast distance lens VA to the high contrast distance lens VA obtained at the Dispensing Visit. If the VA has decreased by 10 letters (0.2 logMAR) or more, explain.

- d. Perform a slit lamp examination (remove the lenses if the subject wore lenses to the visit and place the lenses in a lens case provided filled with Bausch + Lomb Biotrue™ multi-purpose solution). Reconfirm subject eligibility. If eligible, continue the 2-Week Follow-up Visit. If the subject is determined to be ineligible, they must be discontinued and the reason recorded on the Subject Exit Form.
- e. If subject is still eligible, the subject will re-insert the study lenses (the same pair initially dispensed).

Provide subjects with the remaining two surveys and remind the subjects to complete the Take Home Lens Performance Surveys each week for the remaining two weeks. These surveys must be completed each week after a minimum of 5 days of experience with the study lenses and be returned at their next visit.

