#### Secondary Effectiveness Endpoints

- Lens performance survey (100 point scales) questions.

Study ROC2-17-014 - Protocol

- Comfort upon insertion
- Overall comfort
- Comfort at end of day

Secondary Safety Endpoints

- The proportion of subjects with any slit lamp findings grade 2 or greater at any time.

[figure not shown]
Hypotheses

The following hypotheses will be tested for each question in the take home performance questionnaire at each week.

1. The null hypothesis is that the proportion of subjects providing a response in the top three categories is equal between the treatment groups.
2. The alternative hypothesis is that the proportion of subjects providing a response in the top three categories is not equal between the treatment groups.

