#### 7.5 Study Populations

Subject eyes will be included in all summaries under the treatment that they actually received. Analyses of safety data will include all dispensed subjects. All other summaries will include all eligible, dispensed subjects.

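### The 2-Week eligibility re-check can force exit for slit lamp findings that 3.3.3 leaves to discretion, and the efficacy set does not say when eligibility is judged

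*Combined protocol and SAP*

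**What the plan says.** Section 5.2.3, step d, places the slit lamp examination at about two weeks of study-lens wear and follows it with an eligibility check: "Reconfirm subject eligibility. If eligible, continue the 2-Week Follow-up Visit. If the subject is determined to be ineligible, they must be discontinued". Step e continues on the same footing: "If subject is still eligible, the subject will re-insert the study lenses". Neither step limits the check to facts that held at entry.

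The eligibility criterion that a slit lamp tests most directly is exclusion 11 in 3.3.1.2: "Subjects with any grade 2 or greater finding during the slit lamp examination". The same item excludes corneal infiltrates of any grade.

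Section 3.3.3 treats findings during the study differently. Its only slit lamp entry is "persistent grade 3 or 4 slit lamp findings", placed in the list of reasons for which a subject may be discontinued. Its list of mandatory reasons includes ineligibility, but at baseline. The closing paragraph of 3.3.1.2 likewise requires discontinuation of a subject later found not to have met the criteria at entry.

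On the analysis side, 7.5 keeps all dispensed subjects for safety and then says: "All other summaries will include all eligible, dispensed subjects". Section 7.6 repeats the restriction for eyes, pools completed and discontinued eyes, and states that missing data are not imputed. The secondary safety endpoint in 7.2 uses the same threshold as exclusion 11: "The proportion of subjects with any slit lamp findings grade 2 or greater at any time".

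**The concern.** A grade 2 or greater finding is both an exclusion criterion and the safety endpoint. If the 2-Week re-check applies exclusion 11 to what is seen on that day, leaving the study depends on an outcome that the study lens may have caused.

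Three things follow:

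- Sites have two defensible readings and could apply different exit rules to the same finding.
- Exited subjects have no surveys for weeks 3 and 4, which are two of the four intervals of the primary endpoint. They are also absent from the 1-Month slit lamp comparison.
- If eligibility in 7.5 and 7.6 is read as status at any time, those subjects could leave every efficacy summary, including weeks 1 and 2, for which their surveys were already collected.

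The plan makes no allowance for this. Section 7.3 expects very few or no dropouts.

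**Working it through.** **1. The passages side by side, for a subject with a new finding at 2 weeks**

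| Finding | 5.2.3 steps d and e, read with exclusion 11 | 3.3.3 and the close of 3.3.1.2 |
|---|---|---|
| Grade 2, or an infiltrate of any grade | Exit mandatory | Not named; mandatory exit for ineligibility refers to baseline or entry |
| Persistent grade 3 or 4 | Exit mandatory | Exit discretionary |

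The left column is an inference, because 5.2.3 does not mention grade 2. Two things support it. The check comes directly after the slit lamp examination. Step b of the Dispensing Visit (5.2.2) also uses nearly the same sequence, and there it plainly refers to status on that day.

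**2. What an exited subject loses**

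- Surveys for weeks 1 and 2: due back at this visit, so collected.
- Surveys for weeks 3 and 4: not collected and not imputed. The Exit Visit (5.2.5) collects refraction, acuity and keratometry, so it does not replace them.
- At-any-time safety endpoint: the week-2 finding counts, because the safety set is all dispensed subjects.
- By-visit Fisher test at 1 month (7.6): the subject is absent.

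**3. The plan's own power figure**

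Inputs from 7.3: n = 130 per group, proportions 0.500 and 0.670, two-sided alpha 0.05.

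Power = Φ[(0.17·√n − 1.96·√(2·0.585·0.415)) / √(0.25 + 0.2211)]

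At n = 130 this is Φ[(1.938 − 1.366)/0.686] = 79.8%, against 80% stated, so the figure is reproduced. With an assumed share of subjects lost in both arms:

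| Share lost | n per group | Power |
|---|---|---|
| 5% | 123.5 | 77.7% |
| 10% | 117 | 75.5% |
| 20% | 104 | 70.4% |

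The loss of power is modest. Selection matters more.

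**4. Selection, under assumed rates**

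The documents give no rate of grade 2 findings, so every input here is an assumption.

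*Model A.* The true top-three proportion is P in both arms, the proportion among removed subjects is q, and a share g is removed.

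Observed = (P − g·q)/(1 − g), so the shift is g·(P − q)/(1 − g).

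With P = 0.60 and q = 0.30:

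- g = 0.10: 0.570/0.90 = 63.3%. g = 0.04: 0.588/0.96 = 61.2%. The gap is 2.1 points. About 13 v 5 subjects of 130 are removed.
- g = 0.15: 0.555/0.85 = 65.3%. g = 0.05: 0.585/0.95 = 61.6%. The gap is 3.7 points.

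The true difference is zero in both cases. The shift vanishes when q = P and changes sign when q exceeds P.

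*Model B.* The proportion is 0.70 without a finding and 0.30 with one, in both arms.

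- Findings in 10% v 5%: all dispensed subjects give 0.90·0.70 + 0.10·0.30 = 0.66 against 0.95·0.70 + 0.05·0.30 = 0.68, a true difference of 2 points.
- Findings in 20% v 5%: 0.62 against 0.68, a true difference of 6 points.
- If 0.50 replaces 0.30, the differences are 1 point (0.68 v 0.69) and 3 points (0.66 v 0.69).

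Removing subjects with findings leaves 0.70 in both arms, so each of these differences becomes zero.

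**The case against.** The best defence is that the protocol, read as a whole, ties ineligibility to entry. Both 3.3.1.2 and the mandatory list in 3.3.3 do so, and 5.2.3 could be a loose repetition of the Dispensing Visit text. This is a fair reading, but step e speaks of a subject who is still eligible, which points to current status, and nothing in 5.2.3 limits the check. The ambiguity stands.

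Four stronger readings are tempting, and the documents do not support them:

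- *A reader might infer that 5.2.3 and 3.3.3 give flatly opposite orders for a grade 2 finding.* They do not. Section 3.3.3 is silent on grade 2, and its discretionary list is expressly not exhaustive. The tension is between mandatory and discretionary exit, and between any grade 2 finding and persistent grade 3 or 4.
- *A reader might infer that the safety endpoint is biased.* As defined in 7.2 it still counts the week-2 finding in all dispensed subjects. Only the by-visit 1-Month comparison loses them.
- *A reader might infer that exited subjects will be dropped from efficacy.* Discontinued eyes are pooled in 7.6, so exit alone removes nobody. Removal also requires reading eligibility as status after dispensing, which 7.5 and 7.6 neither state nor rule out.
- *A reader might take 2 to 4 points as an estimate of bias.* It is an illustration. Model A holds the overall proportion equal in both arms, which makes unaffected wearers of the lens with more findings truly more satisfied. The figure is also small beside the 17-point example in 7.3, and 7.2 says that the primary endpoints are not pass/fail criteria.

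**Conclusion.** The point holds as an inconsistency with a consequence for the analysis. Following 5.2.3 as written, together with exclusion 11, makes exit depend on the safety endpoint, while 3.3.3 and the close of 3.3.1.2 point elsewhere. The certain consequence for any subject so exited is the loss of week 3-4 surveys and of the 1-Month slit lamp result. Loss of week 1-2 efficacy data is possible, through the undated word in 7.5 and 7.6.

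The size and direction of any bias cannot be determined from the documents. They depend on the rate of findings in each arm and on how affected subjects rate their lenses. If the rates are equal and affected subjects answer alike in both arms, or if affected subjects rate their lenses as others do, there is no distortion under Model A. Under the unequal rates assumed above, Model A gives 2 to 4 points towards the lens with more findings, and Model B hides true differences of 1 to 6 points.

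**What to change.** 1. Reconcile exclusion 11 and the closing paragraph of 3.3.1.2 with 3.3.3 and with steps d and e of 5.2.3, and state which criteria the 2-Week re-check covers. No view is offered on which clinical rule is right.
2. In 7.5 and 7.6, define eligible as meeting the criteria at entry, judged from pre-dispensing data, so that no finding after dispensing removes a subject's collected data from the efficacy set.
3. Report exits triggered by slit lamp findings by arm, so that a reader can see how many week 3-4 and 1-Month results are missing for this reason.

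The cost is wording in 5.2.3 or 3.3.3, a short phrase in each of 7.5 and 7.6, and one summary table. The second change protects the analysis set only. If the reconciled rule still requires exit, the week 3-4 data of those subjects remain missing, and the by-arm report is what makes that visible.

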#### **5.2.4 1-Month Follow-up Visit**

**NOTE: All VA measurements MUST be made using a phoropter.**

**NOTE: If the final Take Home Lens Performance Survey is not completed upon arrival, the subject MUST complete this survey before the subject is exited. The Investigator or designee must review both Surveys for completeness before the subject leaves the office.**

**NOTE: If the subject misses this visit, they MUST be discontinued.**

**NOTE: All worn and unworn lenses must be collected.**

- a. Collect the following lens information from the subject:
  - average daily wearing time

Study ROC2-17-014 - Protocol

- average hours of comfortable wear
  - total number of days of lens wear
- b. Complete the Symptoms/Complaints section for the subject's responses **using the Rating Scale included in initial shipment.**
- c. If the subject did not come to the visit wearing one or more study lenses, go to step e. Otherwise, evaluate the lenses (while on eye), and record the following assessments:
- The Investigator or designees will ask and record the subject's responses to the Lens Performance Survey (100-point scales).
  - distance lens VA
  - over-refraction and distance VA
  - lens wettability
  - lens deposits
  - lens centration
  - lens movement

For each eye, compare the high contrast distance lens VA to the high contrast distance lens VA obtained at the Dispensing Visit. If the VA has decreased by 10 letters (0.2 logMAR) or more, explain.

- d. Perform a slit lamp examination (remove the lenses if the subject wore lenses to the visit and place the lenses DRY in a lens case provided for return to the Sponsor).
- e. Fill out the Investigator Questionnaire.

*NOTE: All worn, unworn, dispensed, non-dispensed study lenses are to be returned as directed with the materials provided. Worn lenses will be returned DRY in lens cases.*

- f. The following E- CRFs should be completed.
- 1-Month Follow-up Visit
  - Investigator Questionnaire
  - The subject has completed the trial – proceed to Subject Exit.

### 5.2.5 Exit Visit

- a. Indicate status of the subject on the Subject Exit Form. If the status is "Discontinued" or "Non-dispensed," indicate the PRIMARY (one) exit reason for each eye on the Subject Exit Form.
- b. For all subjects, complete an exit ocular examination without lenses on the eyes. Collect the following assessments:
- spherocylindrical refraction
  - distance BSCVA
  - keratometry
- c. For each eye, compare the final visit high contrast distance BSCVA to the high contrast distance BSCVA obtained at the Screening Visit. If the VA has decreased by 10 letters (0.2 logMAR) or more, explain.

- d. For each eye, compare the final visit keratometry readings to the Screening Visit keratometry readings. If there is a change of 1.00 D or more, explain.
- e. Indicate if a Post-study Follow-up Visit is required and if necessary, schedule the subject accordingly.
- f. The following e-CRFs should be completed.
  - Subject Exit

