#### **5.2.5.2 Unscheduled Visit**

Additional visits may be scheduled, as necessary, to ensure the safety and well-being of subjects. All additional exams should be fully documented in the subject's record and on Unscheduled Visit e-CRFs, as appropriate. Visits intended to fulfill scheduled visit requirements that fall outside the designated scheduled visit range, are not Unscheduled Visits. In these cases, the visit data will be collected and recorded in the appropriate scheduled visit e-CRF.

If a subject is seen for multiple visits during a given visit timeframe, the data from the visit that is intended to meet the protocol requirements for the scheduled visit should be captured on the visit e-CRF. Where such a determination cannot be made, the first visit within the scheduled visit interval will be used for completion of the protocol required scheduled visit e-CRF. Data from any additional visits within a scheduled visit interval will be captured on an Unscheduled Visit e-CRF.

*NOTE: All VA measurements MUST be made using a phoropter.*

- a. Indicate the reason for the Unscheduled Visit.

*NOTE: If the subject is experiencing problems, complete the entire Unscheduled Visit Form. If this visit is to dispense study materials only and the subject is not experiencing any problems refer to Section 5.2.6.*

- b. Collect the following lens information from the subject:
  - average daily wearing time
  - average hours of comfortable wear
  - total number of days of lens wear
- c. Complete the Symptoms/Complaints section within the Unscheduled Visit Form **using the Rating Scale included in initial shipment.**

- d. If the subject did not come to the visit wearing one or more study lenses, go to step e. Otherwise, evaluate the lenses (while on eye) and record the following assessments:
- distance lens VA
  - over-refraction and distance VA
  - lens wettability
  - lens deposits
  - lens centration
  - lens movement

For each eye, compare the high contrast distance lens VA to the high contrast distance lens VA obtained at the visit at which the lenses were dispensed. If the VA has decreased by 10 letters (0.2 logMAR) or more, explain.

- e. Perform a slit lamp examination (remove the lenses if the subject wore lenses to the visit and place the lenses in a lens case provided filled with *Bausch + Lomb Biotrue™ multi-purpose solution*).

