### **5.2.6 Missed Visits**

If a subject misses the 2-Week Follow-up Visit and cannot be seen prior to the start of the visit range for the next scheduled follow-up visit, the 2-Week Follow-up Visit is considered missed and the subject must be exited from the study.

The Investigator or designee must check the missed visit box on the first page of the applicable e-CRF for that visit.

See Section 3.3.5 Lost to Follow-Up for applicable instructions for subjects who do not return for the final 1-Month Follow-Up Visit.

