**7.3 Sample Size**

The sample size will be 130 subjects per group, which is the maximum affordable sample size. This sample size will have a varying ability to detect differences between the groups depending on the proportions. For example, a two-group  $\chi^2$  test with a 0.050 two-sided significance level will have 80% power to detect the difference between a Smaller proportion,  $\pi_1$ , of 0.500 and a Larger proportion,  $\pi_2$ , of 0.670 when the sample size in each group is 130. Additional cases, assuming the same significance level, power, and sample size are shown in the following figure.

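### The Exit Visit set assigned to early leavers names no slit lamp examination, although slit lamp findings are the only listed safety endpoint; the resulting gap is narrow but cheap to close

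*Combined protocol and SAP*

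**What the plan says.** Section 3.3.3 sets the content of the last visit for subjects who stop early: "Exit Visit assessments should be completed for early terminated subjects". Section 5.2.5 step b defines that content. It opens "For all subjects, complete an exit ocular examination without lenses on the eyes. Collect the following assessments" and lists spherocylindrical refraction, distance BSCVA and keratometry.

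Section 7.2 lists one safety endpoint: "The proportion of subjects with any slit lamp findings grade 2 or greater at any time". Section 7.6 compares it between groups visit by visit with Fisher's exact test, and missing values are not imputed. Section 7.5 puts all dispensed subjects in the safety analyses.

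Three other provisions decide who is examined:

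- Section 5.2.6, on a subject not seen before the next visit range opens: "the 2-Week Follow-up Visit is considered missed and the subject must be exited from the study".
- Section 5.2.5.2, a note on the Unscheduled Visit, whose step e is a slit lamp examination: "If the subject is experiencing problems, complete the entire Unscheduled Visit Form".
- Sections 5.2.3 and 5.2.4, step c: a subject who arrives without study lenses is sent to step e. The slit lamp examination is step d.

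**The concern.** The assessment set prescribed for early leavers omits the one examination that the listed safety endpoint needs. A subject who leaves between scheduled visits without reporting a problem can follow the written steps and be released with no slit lamp examination after lenses were dispensed.

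The screening examination cannot fill the gap, because exclusion criterion 11 bars any finding of grade 2 or greater at entry. Adverse event reporting is only a partial safeguard. Corneal staining of grade 3 or more and neovascularization of grade 2 or more are reportable, but both are graded at the slit lamp, so asymptomatic cases are not seen unless someone looks.

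At stake is the completeness of the safety count. The plan does not say whether a dispensed subject with no later examination counts as event-free in the any-time proportion or leaves the denominator. Under either handling, an undetected finding is not counted.

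**Working it through.** **The plan's own figure.** The only calculation in the documents concerns the take-home survey, not the slit lamp endpoint. Section 7.3 states that a chi-square "test with a 0.050 two-sided significance level will have 80% power to detect the difference between a Smaller proportion" of 0.500 and a larger one of 0.670 "when the sample size in each group is 130". With the pooled-variance formula and no continuity correction:

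n = [1.960 × √(2 × 0.585 × 0.415) + 0.842 × √(0.5 × 0.5 + 0.67 × 0.33)]² / 0.17² = 131 per group after rounding up.

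Power at 130 per group is 0.798. The figure reproduces. It has no bearing on the safety endpoint, for which the plan gives no event rate or power.

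**Where a slit lamp examination is named after dispensing.**

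| Route | Slit lamp named? |
|---|---|
| Exit at the 2-Week Visit, arriving in lenses | Yes, 5.2.3 step d |
| Completion at the 1-Month Visit, arriving in lenses | Yes, 5.2.4 step d |
| Either visit, arriving without lenses | Step c leads to step e, past step d |
| Exit at an Unscheduled Visit with a problem | Yes, 5.2.5.2 step e |
| Problem-free, leaves before the 2-Week Visit | None explicitly named |
| Exited for missing the 2-Week Visit | None explicitly named |
| Problem-free, leaves between the 2-Week and 1-Month Visits | No later one named; normally one result from the 2-Week Visit |

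In the Unscheduled Visit the same skip to step e lands on the slit lamp step. In 5.2.3 step e is re-insertion of the lenses, and in 5.2.4 it is the Investigator Questionnaire.

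For the missed 2-Week Visit, the acceptable range is days 10 to 18 and the 1-Month range opens on day 26 (Section 3.5). A visit on days 19 to 25 is still recorded as the 2-Week Visit. The visit is therefore missed only if the subject has not been seen by day 25, more than three weeks after dispensing.

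**Size.** The documents give no dropout rate (Section 7.3 expects almost none) and no slit lamp event rate, so these are assumptions:

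- Early exits at 2% to 5%: 260 × 0.02 = 5.2; 260 × 0.05 = 13.
- Expected missed events at a 3% event rate, if none of those subjects is examined: 5.2 × 0.03 = 0.16; 13 × 0.03 = 0.39, in the whole trial.
- Wider event-rate range of 2% to 10%: 5.2 × 0.02 = 0.10 up to 13 × 0.10 = 1.3.
- Events per arm at 3%: 130 × 0.03 = 3.9. One missed event would be 1/130 = 0.77 percentage points.

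For a given event rate these counts err high for early leavers, since many early exits do include an examination. They exclude attenders without lenses, whose number the documents do not allow one to estimate.

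**Extreme case.** Take equal observed events in the two arms at an assumed 2%, 5% or 10%, and count every unmeasured subject as an event in one arm and none in the other, out of 130 per arm.

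| Unmeasured per arm | Fisher p over the three event rates |
|---|---|
| 1 (1%) | 1.00 |
| 3 (2%) | 0.50 to 0.69 |
| 6 (5%) | 0.10 to 0.33 |
| 13 (10%) | 0.002 to 0.032 |

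**The case against.** The best defence is that Exit is written as an add-on. Completers reach it from the 1-Month Visit, and the 2-Week and Unscheduled Visits provide for exit on the spot; each of these visits has its own slit lamp step. Section 3.3.3 also asks sites to try to schedule a final study visit and to collect as much follow-up data as they can. The Unscheduled Visit note contrasts subjects with problems with visits made only to dispense materials, and an exit is not such a visit. Section 5.2.7 adds that any assessment made at a resupply visit moves it to the Unscheduled Visit form. Appendix A, the visit schedule, is not visible and may list a slit lamp examination at exit.

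Much of this stands, and it limits the point. A reader might infer that early leavers in general have no safety measurement. The documents do not support that: those who exit at a visit are normally examined there, and those who leave after the 2-Week Visit normally have one on-lens result that counts towards an any-time endpoint. A reader might also take the slit lamp step in the Post-Study Visit (5.2.8) as proof of an oversight at Exit. It is not proof, because that visit stands alone and needs its own examination.

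What the defence does not do is name the examination for a problem-free leaver. The full Unscheduled Visit form is expressly required only for subjects with problems, the 5.2.7 sentence is written for resupply, and the set that 3.3.3 names lacks the slit lamp. If Appendix A does list it, the schedule and 5.2.5 disagree and still need reconciling.

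**Conclusion.** The point holds in a limited form. The written steps leave three groups without a clearly required slit lamp examination: problem-free subjects who leave before, or are exited for missing, the 2-Week Visit; those who leave later between visits, who lack only a later examination; and subjects who attend the 2-Week or 1-Month Visit without lenses.

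The effect is small. Under the assumed 2% to 5% early exit and 3% event rate, fewer than one event would be expected to be missed among early leavers. The expectation passes one only if the event rate among 13 unexamined leavers exceeds 1/13 = 7.7%. At up to 6 unmeasured subjects per arm, even the extreme case does not produce a nominally significant difference; at 13 per arm it could, but that is far from the near-zero dropout the plan expects.

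It is tempting to conclude that the lens with more early exits would look safer. That is not shown. The gap concerns subjects who report no problem, while those with problems have a route that includes the examination. Nothing in the documents says that unexamined leavers would differ by arm or have more findings. The case for change is a complete safety count at little cost.

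**What to change.** - In 5.2.5 step b, add a slit lamp examination by the Appendix B method, unless one was already done at the same visit, and record it on the e-CRF. This also catches subjects who exit at the 2-Week or 1-Month Visit without lenses.
- In 5.2.3 and 5.2.4, correct the skip at step c so that it does not bypass the slit lamp step.
- Reconcile Appendix A and 3.3.3 with the revised 5.2.5.
- In 7.2 and 7.6, state that exit examinations count towards the any-time endpoint, how they enter the by-visit comparison (for example, as a separate exit/unscheduled category), and how a dispensed subject with no later examination is treated in the denominator.

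The cost is a few minutes per affected subject, one e-CRF panel and a few lines of text. Sites already perform this examination. The change cannot supply data on subjects who never return.
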